 72 follows a fractional factorial design as shown in Figure 1. Participants will be recruited
 73 primarily from the community and from clinics serving MCI population across five sites:
 74 London (lead and sponsor site), Waterloo-University of Waterloo, Waterloo-Wilfrid
 75 Laurier University, Montreal, and Vancouver. All eligible participants will be randomized
 76 to 5 arms in 1:1:1:1:1 ratio:

[figure not shown]
77 Arm 1: combined AE and RT exercise + cognitive training + vitamin D

78 Arm 2: combined AE and RT exercise + cognitive training + placebo vitamin D

79 Arm 3: combined AE and RT exercise + control cognitive training + vitamin D

80 Arm 4: combined AE and RT exercise + control cognitive training+ placebo vitamin D

81 Arm 5: BAT exercise + control cognitive training + placebo vitamin D

82 AE: aerobic exercise; RT: progressive resistance training; BAT: balance and toning control

83 Figure 1. Trial design overview

84 5. Study Endpoint

85 The study endpoint will be at 6 Month (post-intervention).

86

87

6. Study Assessment

88 The participant's eligibility will be assessed during the screening visit. Assessment
 89 which will be performed during three visits: baseline, post-intervention at 6 months, and
 90 6-month follow up after the postintervention at 12 months. The measures at each
 91 assessment are described in Table 1.

92

93 Table 1. Assessments across study visits

Procedure	Visit 1 Screening	Visit 2 Baseline	Visit 3 6 month	Telephone Follow-up at 9 month	Visit 4 12 month
Written Informed Consent	X				
Demographic Information	X				
Mini Mental State Examination (MMSE)	X				
Physical Activity Readiness Questionnaire Plus (PARQ +)	X				
Logical Memory 1 & 2	X				
CERAD Word List Recall	X				
PASE Questionnaire	X				
Montreal Cognitive Assessment (MoCA)	X		X		X
Generalized Anxiety Disorder 7 (GAD-7)	X		X		X
Geriatric Depression Scale (GDS-30)	X		X		X
Clinical Dementia Rating (CDR)	X		X		X
Activities of Daily Living (ADCS-ADL and IADL)	X		X		X
Clinical Medical Questionnaire		X	X		X
Dual Task Control Assessment		X	X		X
ADAS-Cog 13 (+ tests ^a)		X	X		X
Trail Making Test A & B ^a		X	X		X
Digit Symbol Test ^a		X	X		X
Digit Span Forward and Backward WAIS-III ^a		X	X		X
Boston Naming Test ^a		X	X		X
Verbal Fluency Test ^a		X	X		X
Colour Word Interference Test		X	X		X
Quality of Life Questionnaire (SF-36)		X	X		X
Short Physical Performance Battery (SPPB)		X	X		X
Gait Assessment using Gait Mats and accelerometers (when available)		X	X		X

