186 coded, using the control group as a reference category. The interaction term will be

187 used to assess between-group differences (representing a mean difference in change in
188 cognitive scores over time between two groups). With dummy coding of the intervention
189 arm, the interaction term will allow to compare the mean change in each intervention
190 arm to the arm 5 (control). The within-group difference (representing a mean change in
191 cognitive scores over time within the group) will be measured with marginalized mean
192 from the linear mixed regression model. The model will be further adjusted for
193 participant characteristics including age, sex, education, and comorbidities.

194 An unstructured covariance matrix will be used for all models. The model assumption
195 will be assessed using the normal quantile plots of residuals for normality and the
196 residuals vs. fitted plot for variance homogeneity. If the assumptions are not fully met,
197 the data will be transformed (i.e., log). Missing data will not be imputed and will be
198 assumed to be missing at random, as the mixed model approach is well-known to
199 handle such data effectively.⁶ The baseline data from individuals who did not complete
200 Month 6 assessment will be included in the linear mixed model.

201 The mean difference between groups will be presented with their 95% CI and p-value,
202 while the mean change within group will be presented with their standard error. The
203 obtained marginalized mean and standard deviation will be used to calculate the effect
204 size (
$$\frac{\text{mean change in treatment } X - \text{mean change in treatment } Y}{\text{pooled standard deviation of change}}$$
). As outlined in our published
205 protocol, we will calculate the proportion of participants with improvement in primary
206 outcomes.

207 All tests will be two-sided, and p-value of less than 0.05 will be considered as
208 statistically significant. Adjustments for multiple comparisons will not be made as the
209 trial is intended to compare the intervention effect to the control rather than pairwise.⁷
210 Per-protocol analysis will be performed as well.

211 As per recommended analyses of fractional factorial design⁸, “at the margin” analyses
212 will be performed by collapsing arms according to the pre-specified comparison.
213 Collapsing intervention arms allow to increase the study power to detect the difference

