214 in effect. More details are provided below for each pre-specified comparison.

215 10.2.1 Effect of aerobic-resistance exercise

216 To address objective 1 (the effect of supervised aerobic-resistance exercise on
217 cognitive function), the intervention arms providing exercise intervention (arm 1 to 4) will
218 be collapsed as one category and compared to the control (arm 5). The new
219 independent variable will be created to represent exercise intervention: aerobic-
220 resistance exercise intervention (collapsed arm 1 to 4), and control exercise intervention
221 – BAT – (arm 5). The new intervention variable will be fitted into the same linear mixed
222 model described above. Using the interaction between exercise intervention x time, the

223 change in primary outcome will be contrasted between participants receiving the
224 aerobic-resistance exercise and those not receiving the aerobic-resistance exercise.

225 10.2.2 Effect of adding cognitive training

226 The objective 2 (the effect of adding cognitive training to aerobic-resistance exercise on
227 cognitive function) will be examined by pooling the intervention arms providing both
228 exercise and cognitive intervention (arm 1 and 2) and pooling the intervention arms
229 providing exercise intervention but not cognitive intervention (arm 3 and 4). A new
230 independent variable will be created for addition of cognitive training: both exercise and
231 cognitive intervention (pooled arm 1 and 2) and exercise but no cognitive intervention
232 (pooled arm 3 and 4). Using the interaction term in the linear mixed model, the contrast
233 will be made between the two collapsed arms to assess whether the effect of adding
234 cognitive training to aerobic-resistance exercise differ from aerobic-resistance exercise.
235 If there is a significant difference observed, the two collapsed arms will be compared to
236 the control arm (arm 5). This marginal analysis will allow to evaluate the main effect of
237 aerobic-resistance exercise alone (pooled arm 1 and 2) and aerobic-resistance exercise
238 with cognitive training (pooled arm 3 and 4) compared to the control (arm 5) with higher
239 power (as a result of increase in sample size).^{5,8}

240 10.2.3 Effect of adding vitamin D supplements

241 The objective 2 (the effect of adding vitamin D to aerobic-resistance exercise on
242 cognitive function) will be examined by pooling the intervention arms providing both

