243 exercise and vitamin D intervention (arm 1 and 3) and pooling the intervention arms
244 providing exercise intervention but not vitamin D (arm 2 and 4). A new independent
245 variable will be created to represent addition of vitamin D: both aerobic-resistance
246 exercise and vitamin D intervention (pooled arm 1 and 3) and aerobic-resistance
247 exercise but no vitamin D intervention (pooled arm 2 and 4). The linear mixed model will
248 be repeated using this new independent variable and the two pooled arms will be
249 compared. This will allow to explore whether adding vitamin D to aerobic-resistance
250 exercise improve the outcome compared to the aerobic-resistance exercise. If a
251 significant difference is observed, the two pooled arms will be compared to the control
252 arm (arm 5) to assess the main effect.

253 10.2.4 Effect of multidomain intervention

254 The objective 4 (effect of multi-domain intervention (aerobic-resistance exercise +
255 cognitive training + Vitamin D supplement) on cognitive function) will be assessed using
256 the time x intervention arm interaction fitted in the linear mixed model in section 10.2.
257 The interaction term between time x intervention arm 1 will represents the effect of
258 multidomain intervention (arm 1) compared to the control (arm 5).

259 **10.2.5 Long-term effect: From Baseline and Post-intervention to Follow up**

260 The long-term intervention effect from baseline and post-intervention to follow-up
261 (Month 12) will be assessed using the linear mixed model. Time will be used as a
262 categorical variable (Baseline, Month 6, and Month 12). Individuals with incomplete
263 follow up assessments will still be included in the linear mixed model.

264 **10.2.6 Post-hoc analyses**

265 ADAS-Cog-Plus is a construction proposed originally by Skinner et al.⁹, adding extra
266 tests for executive function and verbal fluency to increase sensitivity to detect
267 progression from MCI to dementia. Post hoc analyses will be performed to explore the
268 effect of intervention on ADAS-Cog-Plus scores by adding individual Plus items, one by
269 one, to ADAS-Cog-13.

270 **10.3 Secondary Outcomes Analyses**

271 The secondary analysis will be performed in an intention-to-treat population and a per-
272 protocol population. The details of the statistical analysis plan for secondary outcomes
273 are not included in this analysis plan as the secondary outcome analyses will not be

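### SAP 10.2.2 and 10.2.3 report the two-arm pools against control only after a significant add-on margin, so the estimates that appear are selected; the margin models also leave out the other factor, at a small cost

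*Combined protocol and SAP*

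**What the plan says.** SAP 10.2 specifies a mixed model with time, arm and time x arm, and names change at month 6 against arm 5 as its main question. It adjusts further for "participant characteristics including age, sex, education, and comorbidities", tests at two-sided 0.05 and makes no multiplicity adjustment.

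The margins come from separate refits on a recoded variable:

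- **10.2.1, exercise.** Arms 1-4 are pooled against arm 5: "The new intervention variable will be fitted into the same linear mixed" model. There is no condition.
- **10.2.2, cognitive training.** The two levels are exercise plus "cognitive intervention (pooled arm 1 and 2) and exercise but no cognitive intervention" (pooled arms 3 and 4). Then: "If there is a significant difference observed, the two collapsed arms will be compared to" arm 5. The reason given is higher power from the larger pools.
- **10.2.3, vitamin D.** The model will "be repeated using this new independent variable and the two pooled arms will be" compared (1+3 against 2+4). Then, if a "significant difference is observed, the two pooled arms will be compared to the control" arm.
- **10.2.4, multidomain.** Arm 1 against arm 5 is read directly from the five-arm model.

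Neither 10.2.2 nor 10.2.3 lists a term for the other add-on. The gated sentence in 10.2.2 also reverses the labels it has just defined, referring to "aerobic-resistance exercise alone (pooled arm 1 and 2) and aerobic-resistance exercise" with training as arms 3 and 4. SAP 4 allocates "to 5 arms in 1:1:1:1:1 ratio".

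**The concern.** Whether exercise with training, or without it, beats control is a different question from whether training adds to exercise. The plan lets the second decide whether the first is answered, although comparison with arm 5 is its stated priority and the pools exist to make that comparison more precise.

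Two consequences follow. If an add-on does nothing, its pools are not compared with control in about 95% of trials. When they are compared, the arm means have already been sorted by the gate, so one pool looks too good and the other too poor. A reader given an ordinary estimate and 95% CI cannot see this.

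Separately, a margin fitted on one collapsed variable carries the other factor as unmodelled variation. If month-6 completion differs across arms 1-4, part of that factor's effect can enter the margin.

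**Working it through.** **Inputs.** From the documents: two-sided alpha 0.05, d about 0.5, 15% attrition, 40 per arm (SAP 7 and 10.2), and 34 evaluable per arm (protocol 5.3). Assumed, because the documents give no effects by factor: the true add-on effects and the completion patterns. Changes are in SD units with SD known, and positive means benefit.

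**The plan's own figure.** Per side of a margin, 2 x (1.96 + 0.8416)^2 / 0.5^2 = 62.8, so 63. Two arms form a side, giving 32 per arm, and 32/0.85 = 37.6, so 38. The SAP states 40. The protocol's 34/0.85 gives 40 exactly. I use 34.

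**Standard errors.**

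- Add-on margin (68 v 68): sqrt(2/68) = 0.171
- Two-arm pool v arm 5 (68 v 34): sqrt(1/68 + 1/34) = 0.210
- Arms 1-4 v arm 5 (136 v 34): sqrt(1/136 + 1/34) = 0.192
- Single arm v arm 5: sqrt(2/34) = 0.243

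**Link between gate and follow-on.** The covariance of the margin with the add-on pool v arm 5 is 1/68. The correlation is (1/68)/(0.1715 x 0.2100) = 0.41, and -0.41 for the pool without the add-on. The regression slope on the margin is (1/68)/(2/68) = 1/2, so each pool takes half of the margin's selection bias, with opposite signs.

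**Selection bias when the gate opens in favour of the add-on.** For a true add-on effect t, let c = 1.96 - t/0.1715. The margin's bias is 0.1715 x phi(c)/(1 - Phi(c)).

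| t | c | P(opens in favour) | Margin bias | Bias per pool |
|---|---|---|---|---|
| 0 | 1.96 | 0.025 | 0.401 | +/-0.20 |
| 0.25 | 0.50 | 0.308 | 0.196 | +/-0.10 |
| 0.50 | -0.96 | 0.830 | 0.052 | +/-0.03 |

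Simulation of five arm means agrees. With an exercise effect of 0.5, the pools read 0.70 and 0.30 at t = 0 (truth 0.50 for both), 0.85 and 0.40 at t = 0.25 (truth 0.75 and 0.50), and 1.03 and 0.47 at t = 0.5 (truth 1.00 and 0.50).

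**Error rates with no true effects (simulation).** Given an open gate, each follow-on test is falsely significant about 14% of the time and at least one of the two about 27.5% (8.5% without the gate). The gate opens 5% of the time, so the gate plus a false follow-on occurs in about 0.05 x 0.275 = 1.4% of trials for one margin, and 2.7% over both. Without gates, the chance of at least one false positive among the four pooled pairs is 11.3%.

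**Omitting the other factor.** With equal arms and a vitamin D effect of 0.5 SD, the training margin is unbiased. The residual SD rises by sqrt(1 + 0.5^2/4) = 1.031, and power at d = 0.5 falls from 83.0% to 80.7% (normal approximation). With completers n1 to n4, the leakage into the training margin is 0.5 x [n1/(n1+n2) - n3/(n3+n4)]:

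- 37/31/31/37: 0.04 SD
- 36/28/28/38: 0.5 x (36/64 - 28/66) = 0.07 SD
- 40/28/28/40: 0.09 SD
- Dropout driven by one factor only (28/28/38/38 or 28/38/28/38): 0
- Random 15% dropout from 40 per arm: median 0.011 SD, 95th percentile 0.033 SD; 0.07 SD arises in about 1 in 10,000 trials

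**What a pool against control contains.** Half of each training pool receives vitamin D. With equal arms, a vitamin D effect of 0.5 and nothing else, each training pool differs from arm 5 by 0.25 SD. This holds with or without the gate.

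**The case against.** The strongest defence is that the gate limits extra unadjusted tests and hides little. If training adds nothing, the natural exercise estimate is arms 1-4 against arm 5, which always runs and is more precise (SE 0.192 against 0.210). Every single arm is also compared with arm 5, so the pooled point estimates can be recovered approximately by averaging. At the effect the trial was sized for, the gate opens in 83% of trials and the bias is 0.03 SD against an SE of 0.210.

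All of this stands, and it limits the point. It does not justify the gate. The SAP gives no multiplicity rationale for the condition and disclaims adjustment, and the bias is largest where an add-on does little.

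A reader might infer three stronger things that the documents do not support:

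- **That the gate inflates type I error.** It does not. The 14% and 27.5% are conditional on an event with 5% probability, and the unconditional figure is 2.7% over both margins.
- **That pooled exercise against control is lost.** SAP 10.2.1 reports it without condition.
- **That the two margins are confounded with each other.** Equal allocation balances the add-ons within arms 1-4. Appreciable leakage needs dropout concentrated in the arms with exactly one add-on (or in the other two), and nothing in the documents suggests that.

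**Conclusion.** The point holds for the four two-arm pools against arm 5. As written, they appear only when selected, with a bias per pool of about 0.20 SD at no add-on effect, 0.10 SD at 0.25 SD and 0.03 SD at 0.5 SD, in opposite directions for the two pools. This rests on 34 evaluable per arm, normal arm means and assumed effects. The harm is selective and distorted estimates. It does not extend to false claims overall or to the ungated comparisons.

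Leaving the other factor out of each margin model is a minor inefficiency (about 80-81% power against 82-83% at d = 0.5 for both factors), with typical leakage of about 0.01 SD if completion happens to be unequal. It would not justify a change alone, but the same rewording removes it.

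**What to change.** 1. Fit the five-arm model of SAP 10.2 once per primary scale. Take every comparison as an equal-weight contrast of its time x arm terms (arms 1 to 5): training [1/2, 1/2, -1/2, -1/2, 0]; vitamin D [1/2, -1/2, 1/2, -1/2, 0]; exercise [1/4, 1/4, 1/4, 1/4, -1]; and the pairs 1+2, 3+4, 1+3 and 2+4, each against arm 5.
2. Delete both conditions on significance in 10.2.2 and 10.2.3.
3. Report the four pooled-pair estimates with 95% CIs whatever the margin's p-value, as supportive estimates not used to claim efficacy.
4. Label each as an average over the other factor, since it contains half of that factor's effect. The contrast form does not remove this.
5. Correct the reversed pool labels in 10.2.2.

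The cost is SAP wording and four more estimates in the table. No extra participants are needed, and fewer models are run. The downside is that, read as unadjusted tests, the four pairs carry an 11.3% chance of at least one false positive against 2.7% with the gate. That is why item 3 keeps them out of the efficacy claim.

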2. STUDY DESIGN AND HYPOTHESES

2.1. HYPOTHESES

2.1.a Primary Hypotheses

1. Twenty weeks (five months) of supervised multimodal exercise (aerobic and progressive resistance training) alone and/or in combination with cognitive training (CT) and/or oral vitamin D will significantly improve global cognitive function in older adults with MCI, as assessed by primary outcome **Alzheimer's Disease Assessment Scale-Cognitive subscale plus (ADAS-Cog Plus)**.
2. Multimodal exercise alone and/or in combination with CT and/or oral vitamin D would significantly improve secondary cognitive outcomes across memory, executive function, and attention, as well mobility outcomes related to falls risk and dual-task gait, and dual-task gait cost.

3. The combination of CT and oral vitamin D with multimodal exercise will be significantly superior to either intervention alone for cognitive and functional benefits, demonstrating a synergistic effect.
4. Mechanistically, our intervention will significantly improve hippocampi volume, blood biomarkers, and BDNF levels [24], and fMRI prefrontal activation in executive control dual-task condition.

2.1.b Secondary Hypotheses

1. All active training interventions will improve brain morphology and biochemistry compared with control –placebo-interventions as defined by: increased hippocampal volume (mm^3) by MRI scanning; positive localized Voxel-Based Morphometry (VBM) brain changes (z-score relative change); decreased whole brain volume of White Matter Hyper-intensities (WMHs) (mm^3); and lead to beneficial hippocampal and anterior and posterior cingulate MRS metabolite changes (% increase in N-acetylaspartate, and increase in phosphocreatine metabolites).
2. All active interventions will improve secondary cognitive outcomes, in the domains of attention, memory, fluency, and executive function, relative to the control condition, and combined training will be superior to either single intervention.
3. Multimodal exercise will preferentially decrease inflammatory markers, and increase fitness (strength and aerobic capacity), muscle strength, and functional mobility, compared to either cognitive or control condition.
4. Cognitive and physical training will produce positive effects on psychological health and quality of life (SF-36) above and beyond the non-specific effects seen after control condition.

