8. ANALYSIS

Analysis, planned analysis, frequency of analysis, and correction for multiple testing

Analysis will be conducted as intention to treat and as per-protocol analysis. For the primary endpoint (ADAS-Cog plus), the change from baseline to six months and 12 months will be assessed using a repeated measures analysis of covariance (ANCOVA) model incorporating the baseline values as covariates. Observing a statistically significant difference in the primary outcome will be considered preliminary evidence of efficacy. Additionally, reduction of prevalence rate of abnormal ADAS-Cog plus score (dichotomous variable) will be assessed as a primary outcome.

We will also report variances, co-variances, and effect sizes, as well as sampling feasibility (i.e., ease of recruitment, recruitment rate, withdrawal rate). Descriptive statistics for demographic and baseline characteristics will be provided with means and standard deviations, or medians and the interquartile range where appropriate, for continuous characteristics and frequencies and percentages for categorical variables.

If the within-group comparison is statistically significant, Tukey's multiple comparisons will identify significant pairwise differences. Similarly, for the secondary endpoints, six month changes in gait performance and secondary cognitive outcomes of interest will be performed using one way analyses of variance. For group comparisons that are statistically significant, pairwise comparisons will be made using Tukey's multiple comparisons tests. All statistical tests will be two-tailed, and a *p*-value of less than 0.05 will be considered to indicate statistical significance. All calculations will be made using SPSS software package version 23.0 (SPSS Inc., Chicago, IL).

Secondary analyses will be also performed according to an intention-to-treat principle and per protocol analysis. Frequency of the analyses: preliminary analysis will be performed at month 6 to ascertain descriptive characteristics at baseline assessment. Final efficacy analysis will be performed at the end of the trial since no safety issues are involved in this study. The statistical significance of the results will be

determined by Hochberg's variation of the Bonferroni procedure for multiple testing.³⁹ An economical analysis will be also performed addressing health resources utilization.

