35 and vitamin D supplementation on cognitive function.

36 Specifically, physical exercise is a progressive and supervised aerobic (AE) and
37 resistance training (RT) program tailored for older adults' physical capabilities.
38 Computerized cognitive training will be delivered using the Neuropeak cognitive training
39 program designed to target working memory and attention. Vitamin D supplementation
40 will be delivered in capsules with 10,000 IU, 3 times per week, reaching a weekly dose
41 of 30000 IU. Control interventions will be sham cognitive training, balance and toning
42 exercise (BAT), and matching vitamin D placebo capsules.

43

44 2. Study Objectives

45 To evaluate:

46 **Objective 1** The effect of supervised aerobic-resistance exercise on cognitive function

47 **Hypothesis 1.** Twenty weeks of supervised aerobic-resistance exercise will significantly
48 improve cognitive function in older adults with MCI, as assessed by primary outcome
49 Alzheimer's Disease Assessment Scale-Cognitive (ADAS-Cog 13 and plus variant) and
50 secondary outcomes, compared to a balance and toning (BAT) control.

51 **Objective 2.** The effect of adding cognitive training to aerobic-resistance exercise on
52 cognitive function.

53 **Hypothesis 2.** Adding cognitive training to aerobic-resistance exercise will significantly
54 improve primary and secondary outcomes compared to aerobic-resistance exercise
55 without cognitive training.

56 **Objective 3.** The effect of adding vitamin D supplementation to aerobic-resistance
57 exercise on cognitive function.

58 **Hypothesis 3.** Adding vitamin D supplementation in weekly dose of 30000 IU to
59 aerobic-resistance exercise will significantly improve primary and secondary outcomes
60 compared to aerobic-resistance exercise without vitamin D supplementation.

61 **Objective 4.** The effect of multi-domain intervention (aerobic-resistance exercise +
62 cognitive training + Vitamin D supplementation) on cognitive function.

63 **Hypothesis 4.** The multi-domain intervention (aerobic-resistance exercise + cognitive
64 training + vitamin D supplementation) will significantly improve primary and secondary
65 outcomes compared to the control intervention.

66

67 3. Study Population

68 We will target older adults aged 60 to 85 years old with mild cognitive impairment (MCI).

69

70 4. Study Design

71 This is a Phase II, randomized, double-blind, five-arm controlled trial. The trial design

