Six Minute Walk Test (6MWT) ^b		X	X		X
Neuroimaging (MRI)					
Blood Draw		X	X		
Falls Calendar ^c		X	X	X	X

94 ^aTesting included in the ADAS-Cog plus95 ^bThis test may be completed at the gym facility on the first day of intervention96 ^cCalendar will be given to participant to complete and will be submitted to Research Staff at exercise training97

7. Determination of Sample Size

98 Sample size calculation is based on changes in our primary outcome: global cognitive
 99 function measured using the Alzheimer Disease Assessment Scale Cognitive 13 and

100 the plus variant (ADAS-Cog 13 and plus). A target sample of 200 participants (40 per
 101 arm) was determined based on 80% power to detect either main effects or an
 102 interaction of at least a moderate (Cohen's $d \sim 0.5$)¹ effect size of changes in the ADAS-
 103 Cog-13.² The final sample size accounted for a 15% attrition.

104

105 **8. Primary Outcomes**

106 Primary outcome will be changes in cognitive function measured with the ADAS-Cog 13
 107 items (ADAS-Cog-13) and the plus variant (ADAS-Cog-plus) at endpoint, 6 Month.
 108 Improvement at endpoint in either variant is considered evidence of efficacy.

109 **8.1 Change in cognitive function on ADAS-Cog-13 at post-intervention (Month 6)**

110 The ADAS-Cog 13 consists of 13 brief cognitive tests assessing memory, language,
 111 attention, concentration and praxis. The individual tests are listed in Table 2. Scores
 112 range from 0 to 84, with higher scores indicating severe cognitive impairment.

113 **8.2 Change in cognitive function on ADAS-Cog-Plus at post-intervention (Month 6)**

114 Four additional tests focusing on executive function will be added to the ADAS-Cog 13
 115 to comprise the plus variant³ (Table 2). Scores will be transformed into an algorithm
 116 validated by Crane et al.⁴ The higher scores will indicate severe of cognitive impairment.

117
 118 Table 2. Individual tests included in the ADAS-Cog

ADAS-Cog-13	ADAS-Cog-Plus
Word recall	Word recall
Delayed word recall	Delayed word recall
Following commands	Following commands
Constructional praxis	Constructional praxis
Ideational praxis	Ideational praxis
Naming objects	Naming objects
Orientations	Orientations
Word recognition	Word recognition
Remembering instructions	Remembering instructions
Comprehension	Comprehension
Word finding	Word finding
Spoken language	Spoken language
Number cancellation	Number cancellation
	Trial Making A and B
	Digit symbol substitution

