153 AP/PA correction scan = 7 min) to calculate fractional anisotropy and diffusivity in white
154 matter tracts as well as derive tract-based statistics. Cerebrovascular integrity and
155 pathology will be assessed using the following contrasts: PD/T2 = 5 min; FLAIR = 7 min,
156 and T2* = 5 min). Functional magnetic resonance imaging at rest (rsfMRI plus field map
157 = 12 min) will also be acquired to measure change in data-driven functional networks.

158 **9.5 Change in Blood biomarkers measures**

159 Serum biomarkers of inflammation (C reactive protein, and interleukin 6), neuroplasticity
160 (brain-derived neurotropic factor), endothelial health (vascular endothelial growth factor
161 1), and vitamin D serum levels will be measured before and after intervention.

162 **9.6 Covariates**

163 Pre-specified covariates will be age, sex, years of education and number of
164 comorbidities.

165

166 **10. Statistical Analysis**

167 **10.1 Descriptive Analysis**

168 The baseline characteristics will be summarized using means and standard deviation, or
169 medians and interquartile range where appropriate, for continuous characteristics, and
170 frequencies and percentages for categorical variable.

171 **10.2 Primary Efficacy Analysis**

172 The primary analysis will be based on the intention-to-treat principle, including everyone
173 who were randomized. Comparisons between arms will be conducted according to pre-
174 specifications in the protocol. These comparisons align well with the recommended
175 analysis and reporting of factorial trials⁵, which used “inside the table” and “at the
176 margin” analyses for different comparisons. The “inside the table” analysis will be used
177 to compare each intervention effect to control, while “at the margins” analysis will be
178 used to assess the effect of adding intervention.

179 The major interest would be the effect of the intervention on change in primary
180 outcomes at 6 Month compared to the control arm (arm 5). The primary outcome
181 measure of mean change in ADAS-Cog-13 and ADAS-Cog-Plus scores will be analyzed
182 using a linear mixed model with restricted likelihood estimation. The model will be fitted
183 with participant-specific random intercept and fixed effects of time, intervention arm, and
184 time x intervention arm interaction. The time variable will be used as a categorical
185 variable (0 = baseline; 1 = Month 6.) The intervention arm variable will be dummy

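### The SAP specifies no CT x vitamin D contrast for the protocol's synergy hypothesis, does not declare it dropped, and its 80% power statement does not hold for the exercise main effect

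*Combined protocol and SAP*

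**What the plan says.** Protocol 2.1.a lists as primary hypothesis 3 that adding CT and vitamin D to exercise "will be significantly superior to either intervention alone for cognitive and functional benefits, demonstrating a synergistic effect". Protocol 1.1 also names synergy as something the trial will test.

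SAP 2 has four hypotheses. The fourth concerns the full combination, and its comparator is control: improvement in primary and secondary "outcomes compared to the control intervention". Synergy is not among the four, and nothing says it was withdrawn.

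SAP 10.2 to 10.2.4 specify these month-6 cognitive analyses:
- each arm against arm 5;
- arms 1-4 pooled against arm 5;
- arms 1+2 against 3+4 (adding CT);
- arms 1+3 against 2+4 (adding vitamin D);
- if an add-on comparison is significant, its pools against arm 5;
- for Objective 4, the "multidomain intervention (arm 1) compared to the control (arm 5".

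On pairwise tests, SAP 10.2 opens with "Comparisons between arms will be conducted according to pre" (the word runs over a line break and becomes pre-specifications in the protocol). Protocol 8 says that, after a significant within-group comparison, "Tukey's multiple comparisons will identify significant pairwise differences"; it also names Hochberg's procedure. Yet SAP 10.2 later makes no multiplicity adjustment, because the "trial is intended to compare the intervention effect to the control rather than pairwise".

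On power, SAP 7 says that 200 participants (40 per arm) "was determined based on 80% power to detect either main effects or an" interaction of at least about d 0.5 on change in ADAS-Cog-13, allowing for 15% attrition.

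**The concern.** A hypothesis that the protocol lists as primary reaches the SAP with no planned estimate for its synergy part and no statement that it was set aside. On its own, arm 1 is named only against arm 5. That difference combines exercise, CT, vitamin D and any synergy, and cannot separate them. If the trial later reports on synergy, or is silent about it, a reader cannot tell which was planned.

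The power sentence adds to this. It covers main effects and an interaction with one figure but does not say which interaction or on what scale. SAP 10.2.2 then describes its pools the wrong way round: it defines arms 1+2 as exercise with CT, but a few lines later calls them exercise alone and calls arms 3+4 exercise with CT. Followed literally, the last sentence would reverse the reported result.

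**Working it through.** **What each planned contrast estimates.** Let the mean month-6 changes, relative to arm 5, be: arm 4 = e; arm 3 = e + v; arm 2 = e + c; arm 1 = e + c + v + i. Here e is exercise, c is CT given exercise, v is vitamin D given exercise, and i is their synergy.

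- Arm 1 - arm 5 = e + c + v + i
- CT margin = (arm 1 + arm 2)/2 - (arm 3 + arm 4)/2 = c + i/2
- Vitamin D margin = (arm 1 + arm 3)/2 - (arm 2 + arm 4)/2 = v + i/2
- Arm 1 - arm 2 = v + i; arm 1 - arm 3 = c + i
- Arm 1 - arm 2 - arm 3 + arm 4 = i

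Only the last isolates synergy. It can be computed from the planned five-arm model but is not specified. Each margin is a valid average of one add-on over the other factor. Superiority over arms 2 and 3 is a different question: with c and v non-zero and i = 0, arm 1 still differs from both.

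**Pairwise tests.** Five arms give 5 x 4 / 2 = 10 pairs, the number used in Protocol 5.3, so the protocol's Tukey step includes arm 1 against arms 2 and 3. Deferring to the protocol imports these tests; the disclaimer in the same SAP section excludes them. Neither route supplies an interaction contrast, because Protocol 8 has none.

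**Power: inputs.** d = 0.5 in units of the SD of change (SAP 7); two-sided 0.05 (SAP 10.2); 40 x 0.85 = 34 evaluable per arm (SAP 7). Assumptions: equal SDs, no gain from covariates, noncentral t.

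**The plan's own figure.** With d = 0.5 and 80% power, a two-group comparison needs 63 per group. A margin pools two arms, so this is 32 per arm, and 32/0.85 gives 38. That is within two of the 34 and 40 planned, so the 80% is consistent with the CT and vitamin D margins.

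**The other readings.** SE = sqrt(1/n1 + 1/n2) for two groups. For the difference of differences, SE = sqrt(4/n).

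| Contrast | SE at 34 per arm | Power at 34 | Power at 40 |
|---|---|---|---|
| CT or vitamin D margin, 68 v 68 | 0.171 | 82.5% | 88.2% |
| Exercise main effect, 136 v 34 | 0.192 | 73.7% | 80.4% |
| CT x vitamin D, difference of differences 0.5 SD | 0.343 | 30.4% | 34.9% |
| CT x vitamin D, effect-coded 0.5 (difference of differences 1.0 SD) | 0.343 | 82.5% | 88.2% |

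Here effect-coded means the mean of arms 1 and 4 minus the mean of arms 2 and 3, which is i/2. For i itself the 95% half-width is 0.678 SD (df 132), and 80% power is reached only at 0.968 SD.

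**The case against.** The strongest reply is that the SAP narrowed the trial deliberately. It sets four objectives, calls the trial phase II and says it compares with control. Protocol 2.1.a also places mobility, imaging and biomarker claims under the same primary heading, so the label alone does not mark a confirmatory test. This limits the weight of the point, and one sentence of withdrawal would meet it. But the remark about pairwise comparisons is given only as the reason for making no adjustment, does not mention hypothesis 3, and sits beside the deference to the protocol.

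A reader could approximate the contrast, "while the mean change within group will be presented with their standard error". That is true, but a contrast that can be derived has no pre-specified status.

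Three stronger readings are tempting, and the documents do not support them:
- **That arm 1 against arms 2 and 3 is clearly absent.** The reference to the protocol may bring those tests in; the fault is an unresolved conflict.
- **That the SAP offers arm 1 against arm 5 as evidence of synergy.** It does not. That contrast answers Objective 4 correctly.
- **That the trial is shown to be underpowered for its interaction.** Every interaction in SAP 10.2 is time by arm or time by pooled group, so reading SAP 7 as CT x vitamin D is an inference. On the effect-coded scale, power is about 82%. SAP 7 also cites a published protocol that may define the contrast; it cannot be seen here.

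The functional part of hypothesis 3 is outside this point, because SAP 10.3 defers secondary outcomes.

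**Conclusion.** The point holds for the cognitive outcome. The SAP neither specifies a CT x vitamin D x time contrast nor says that hypothesis 3 was dropped, and its position on arm 1 against arms 2 and 3 contradicts itself.

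The 80% in SAP 7 is supported for the CT and vitamin D margins. It is not supported for the exercise main effect, which has about 74% after the stated attrition and reaches 80% only if nobody is lost. For the interaction, the documents support only the statement that it is undefined; the choice of scale moves power between about 30% and 82%. The swapped labels in SAP 10.2.2 are a plain error.

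The power figures rest on d = 0.5 in SD-of-change units, 34 per arm, equal variances and no covariate gain. The missing contrast and the label error do not depend on them. The point should be addressed, but it does not invalidate the planned primary comparisons.

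**What to change.** 1. Add to SAP 10.2, from the planned five-arm model, the month-6 change contrast arm 1 - arm 2 - arm 3 + arm 4 with its 95% CI. Label it exploratory, or post hoc if outcome results have been seen. Describe it as CT x vitamin D synergy given exercise only: no arm gives CT or vitamin D without exercise, so synergy with exercise itself cannot be estimated. Alternatively, state that hypothesis 3 is not pursued.
2. Reconcile Protocol 8 with the two statements in SAP 10.2: say whether pairwise tests will be done and whether Tukey, Hochberg or no adjustment applies.
3. Restate SAP 7 as about 82% for the CT and vitamin D margins and about 74% for the exercise main effect after attrition. Name the interaction and its scale, with the matching power.
4. Correct the pool labels at the end of SAP 10.2.2.

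The cost is SAP wording and one contrast from a model already planned, with no new data. The downside is imprecision: with a 95% half-width of about 0.68 SD, wider than the 0.5 SD design effect, a null result would not exclude moderate synergy. Powering a 0.5 SD difference of differences at 80% would need 4 x (1.960 + 0.842)^2 / 0.5^2, or 126 evaluable per arm (149 with 15% attrition). This is why the contrast should be exploratory.
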